[figure not shown]

Pilot Study: Investigating a Novel Supplement-based Therapy for the Treatment of Small Intestinal Bacterial Overgrowth

[name].
Senior Director, Scientific Affairs at Atrium Innovations

Version #2
May 3, 2017

Study Synopsis

The aim of this pilot study is to determine the efficacy of a supplement protocol combined with a low FODMAP diet for the treatment of small intestinal bacterial overgrowth (SIBO). The study is designed as a prospective, open label investigation, with an estimated sample size of 10 patients.

Patients diagnosed with SIBO by [name] at Good Medicine Clinic (Oxford, Ohio) will be offered the opportunity to enroll in this study, if they satisfy the inclusion and exclusion criteria upon initial diagnosis. No control group will be assigned.

The diagnosis of SIBO will be determined via assessment of clinical symptoms and the results of a lactulose breath test. This diagnosis procedure is, currently, the standard-of-care. After administration of the supplement therapy and adherence to a low FODMAP diet (8 weeks), the lactulose breath test will be repeated and symptoms re-assessed by [name].

The post-treatment lactulose breath test and all supplements in the protocol will be provided free-of-charge to enrolled patients. In addition, enrolled patients will not be billed for the mid-treatment office visit. Patient and/or patient insurance will be responsible for all other expenses, including but not limited to the initial breath test, all other office visits and travel.

Background

Small intestinal bacterial overgrowth (SIBO) is a category of gastrointestinal infection, characterized by an increased concentration ($>100,000$ CFU/mL proximal jejunal fluid) of bacteria in the small intestine.¹ Symptoms of SIBO commonly afflict the gastrointestinal tract and include but are not limited to: abdominal pain, discomfort, bloating, cramping, flatulence, diarrhea, constipation, eructation, and low serum B12.^{3,4}

SIBO is believed to be severely under diagnosed and is associated with numerous comorbid conditions including irritable bowel syndrome, diabetes mellitus and hypothyroidism.^{4,5} Small-bowel aspiration (SBA) or breath tests are used to aid in the diagnosis of SIBO. Due to the cost and invasive nature of SBA, glucose or lactulose breath tests are more commonly performed.

The treatment of SIBO frequently consists of antibiotic therapy. Rifaximin is a poorly absorbed antibiotic with bacteriocidal activity against enteropathogens and is widely prescribed for the treatment of SIBO.³ Nevertheless, both patients and practitioners frequently turn to complementary and alternative medicine, due to the adverse effects associated with antibiotic use and the recurrent nature of SIBO. In 2014, a retrospective study (Chedid et al.) found that the efficacy of a particular herbal therapy was comparable to Rifaximin treatment.³ However, both treatment

options demonstrated a response rate of less than 50%. This investigation will test a more comprehensive, supplement-based therapy in hopes of achieving a greater response rate.

Objectives

This investigation aims to determine the efficacy of a supplement protocol in combination with a low FODMAP diet for the treatment of small intestinal bacterial overgrowth (SIBO).

Patient Selection

Patients diagnosed with SIBO at [name] clinic will be offered the opportunity to enroll in this study as a theoretical treatment option for SIBO. Other treatment options will be discussed with the patient. Enrolled patients must satisfy the following inclusion and exclusion criteria:

Inclusion criteria: A positive diagnosis of SIBO, which will be defined by 1) presentation of the aforementioned symptoms and 2) positive results of a lactulose breath test. Positive breath test results will be defined as an increase in hydrogen of 20 ppm or more and/or an increase in methane of 12 ppm or more compared to baseline by 90 minutes.

Exclusion criteria: 1) Use of prescription antibiotics or antifungals within the past 4 weeks. 2) Younger than 18 or older than 85 years of age 3) Pregnant or breast-feeding 4) Major drug-supplement interactions between essential medication and the proposed supplement therapy. 5) A known allergy to one or more of the ingredients in the supplement therapy. 6) Has been diagnosed and treated for SIBO within the past 6 months. 7) Has undergone a colonoscopy or barium enema within the past 4 weeks. 8) Has an allergy to lactulose. 9) Has diabetes mellitus.

Study Procedures

The supplement protocol is designed to take 8 weeks. Due to the delay in receiving and interpreting test results, the investigation, in its entirety, is estimated to take 12 weeks.

Visit -1 [name] will assess patient history and symptoms, at his facility in Oxford, Ohio. If suggestive of SIBO, a lactulose breath test will be prescribed. Additional testing may be performed, at the discretion of [name], to aid in the initial diagnosis of the patient.

Visit 0 [name] will assess the results of the breath test and confirm or deny the diagnosis of SIBO. Treatment options for SIBO will be discussed, and the patient will be made aware of this investigation as a theoretical treatment option. Patient eligibility will be determined by [name] who will complete the Patient Eligibility Checklist (Appendix A) for each patient. All female patients will be asked to complete a urine pregnancy test to confirm pregnancy status. Eligible patients will be asked to review

and sign the Informed Consent document. [name] (Medical Assistant at Good Medicine) will be available to discuss patient consent and confidentiality. Enrolled patients will be asked to complete a baseline Medical Symptom Questionnaire (Appendix B). Afterwards, [name] will review the supplement therapy (Supplement Overview - Appendix C) and low FODMAP diet (Low FODMAP Handout - Appendix D). Patients will then be provided with all supplements necessary to complete the investigation. Patients will be asked to discontinue all other supplements during the study. However, no wash out period is required. Prescription medications, over-the-counter medications and/or supplements deemed medically necessary by the patient's primary care physician and/or [name] may be continued, if there are no known contraindications.

Visit 1 Visit 1 will occur approximately 4 weeks after the patient begins the supplement protocol. Patients will be asked to report their compliancy with the supplement protocol and low FODMAP diet and describe adverse effects. Patients will also be asked to complete the Medical Symptom Questionnaire. Patients will be provided with the second lactulose breath test kit and instructed to perform the test within 2 weeks of completing the supplement therapy.

Visit 2 Visit 2 will occur after the results of the post-treatment breath test are available. [name] will interpret the results of the second breath test, and patients will be asked to complete the Medical Symptom Questionnaire, report compliancy with the supplement protocol and low FODMAP diet, and describe any adverse effects. Further treatment options will be discussed if necessary; follow-up treatment will be outside the scope of this investigation.

Risk/Safety Information

This study presents risk in the form of adverse reactions to ingredients in the supplement therapy. Patient risk will be minimized by excluding patients who may respond poorly to the supplement therapy or testing procedures from the study, i.e., by abiding by the aforementioned patient enrollment exclusion criteria.

Monitoring/Reporting

Patients may report adverse events to Good Medicine during scheduled office visits or by phone during office hours. If serious or life-threatening side effects arise, patients are instructed to call 911. Possible side effects include but are not limited to: diarrhea, constipation, nausea, vomiting, bloating or headache. When necessary, [name] or [name] will communicate with patients outside the office by phone and record adverse events in the patient's confidential files. Medical guidance will be provided as necessary.

Study Oversight

This study will be terminated if one-half or more of enrolled patients withdraw due to adverse events. [name] and [name] (Senior Director, Scientific Affairs at Atrium Innovations) will monitor, determine the need for and facilitate the termination of the study. Direct access to study related data will be made available for monitoring, auditing, IRB review and regulatory inspection.

Data Management

Lactulose breath test scores and completed Medical Symptom Questionnaire will be compared pre- and post-treatment to determine the efficacy of the supplement therapy. The significance of the change in breath test scores will be determined if the final sample size permits such analysis.

IRB Review/Ethics/Informed Consent

This study will be conducted in accordance with the ethical principles that have their origin in the Declaration of Helsinki and that are consistent with Good Clinical Practice and applicable regulatory requirements.

Any changes to the protocol will be submitted to the IRB for review and approval before implementation. However, a protocol change intended to eliminate an apparent immediate hazard to patients will be implemented immediately. The reviewing IRB will be notified within 10 working days, if an immediate protocol change is necessitated.

The principle investigator ([name]) will provide each patient with full and adequate verbal and written information using the IRB approved informed consent documentation, including the objective and procedures of the study as well as the possible risks involved before inclusion in the study. Informed consent will be obtained prior to performing any study-related procedures, including screening and changes in medications including any washout of medications. A copy of the signed informed consent will be given to the study patient.

Confidentiality

Study-related records identifying the patient will be kept confidential and, to the extent permitted by applicable laws and/or regulations, will not be made publicly available. The IRB and/or other regulatory authorities will have access to study related medical records upon request. Subsequent use of the collected data will exclude patient identifying information.

Intended Use of the Data

The data collected from this investigation will be used to determine the efficacy of the proposed supplement therapy. If efficacious, the results will be distributed in print and digital advertising.

References

4. Reynolds K. Small Intestinal Bacterial Overgrowth: A Case-Based Review. *Journal of Patient-Centered Research and Reviews*. 2015; 2(4): 165-171.
5. Saad R and Chey W. Breath Testing for Small Intestinal Bacterial Overgrowth: Maximizing Test Accuracy. *Perspectives in Clinical Gastroenterology and Hepatology*. 2014; 12:1964-1972.

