Appendix C

Small Intestinal Bacterial Overgrowth (SIBO) Protocol

Dietary Recommendations

Follow the low FODMAP diet at the guidance of a healthcare professional. See included Stanford University Medical Center FODMAP handout for a brief introduction to this diet.

Duration

This protocol is designed to take 8 weeks.

Product Overview

Category	Products	Servings per Bottle	Capsules per Day	Duration	Number of Bottles*
Detox Support	Liver-G.I. Detox	60 capsules	2 per day	30 days	One bottle
GI Support	L-Glutamine Powder	73 scoops	2 scoops per day	35 days	One bottle
Microbial Balance	MicroDefense	90 capsules	1 per day	49 days	One bottle
Microbial Balance	A.C. Formula II	120 capsules	4 per day	49 days	Two bottles
Probiotic	Probiotic-5	60 capsules	1 per day	49 days	One Bottle
Digestive Enzymes	Digestive Enzymes Ultra with Betaine HCl**	180 capsules	As needed (up to 6)	Long term	One bottle

*The number of capsules purchased may exceed the amount required by this protocol, due to limited bottle sizes.

**Digestive Enzymes Ultra with Betaine HCl may be replaced with Digestive Enzymes Ultra, if patient responds poorly to Betaine HCl.

Protocol

	Product	Breakfast	Lunch	Dinner
Week 1	Liver-G.I. Detox	1 capsule		1 capsule
	Digestive Enzymes Ultra with Betaine	1-2 capsules or as needed before meal	1-2 capsules or as needed before meal	1-2 capsules or as needed before meal
Weeks 2 – 5	Liver-G.I. Detox (finish 2 days into week 5)	1 capsule		1 capsule
	Digestive Enzymes Ultra with Betaine	1-2 capsules or as needed before meal	1-2 capsules or as needed before meal	1-2 capsules or as needed before meal
	L-Glutamine	1 serving	1 serving	
	A.C. Formula II	2 capsules before meal	2 capsules before meal	
	MicroDefense		1 capsule before meal	
	Probiotic-5			1 capsule
Week 6	Digestive Enzymes Ultra with Betaine	1-2 capsules or as needed before meal	1-2 capsules or as needed before meal	1-2 capsules or as needed before meal
	L-Glutamine	1 serving	1 serving	
	A.C. Formula II	2 capsules before meal	2 capsules before meal	
	MicroDefense		1 capsule before meal	
	Probiotic-5			1 capsule
Weeks 7 & 8	Digestive Enzymes Ultra with Betaine	1-2 capsules or as needed before meal	1-2 capsules or as needed before meal	1-2 capsules or as needed before meal
	A.C. Formula II	2 capsules before meal	2 capsules before meal	
	MicroDefense		1 capsule before meal	
	Probiotic-5			1 capsule

Low-FODMAP Food Plan

PROTEINS

Proteins

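### Visit 1, the only scheduled visit during the 8-week course, does not re-ask about pregnancy, breast-feeding or newly started interacting drugs: a minor gap that is cheap to close

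*Protocol*

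**What the plan says.** Exclusion 3 in Patient Selection rules out pregnant or breast-feeding patients. Exclusion 4 rules out major interactions between the supplements and a medication the patient needs. Both are applied at Visit 0 (Study Procedures): the investigator completes the Appendix A checklist and female patients are asked to take a urine pregnancy test. Appendix A asks about current pregnancy or breast-feeding, about plans for either over the coming 4 months, and about drugs now being taken from a printed list. At the same visit, "Patients will then be provided with all supplements necessary to complete the investigation".

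On timing, Appendix C states "This protocol is designed to take 8 weeks", and Study Procedures states "Visit 1 will occur approximately 4 weeks after the patient begins the supplement protocol". At Visit 1, "Patients will be asked to report their compliancy with the supplement protocol and low FODMAP diet and describe adverse effects". The symptom questionnaire and the breath-test kit complete the list for that visit. Visit 2 waits for the result of the post-treatment breath test.

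Risk/Safety Information says that patient risk is kept down by leaving out patients who may respond poorly, "i.e., by abiding by the aforementioned patient enrollment exclusion criteria". Monitoring/Reporting lets patients report adverse events at visits or by phone, and that paragraph ends "Medical guidance will be provided as necessary".

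**The concern.** Both conditions can change during treatment, but the Protocol looks at them once, before the first dose. Dispensing everything at Visit 0 means that no later supply step would prompt a second look. The medication sentence at Visit 0 deals with drugs that are carried on into the study, not with drugs begun afterwards. No step is stated for a patient who newly meets exclusion 3 or 4.

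At stake is continued dosing of a patient whom the Protocol's own criteria would have kept from starting. If she already knows of a pregnancy by Visit 1, or has begun an interacting drug by then, the visit can be completed as described without the investigator learning of it, unless the patient brings it up. This is a matter of patient safety and has no bearing on the efficacy comparison.

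**Working it through.** The Protocol states no figure on this point, so there is none to reproduce. The check has three parts.

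**1. Is Visit 1 the only visit on treatment?** The course runs for 8 weeks (56 days). Visit 1 is at about 4 weeks (day 28). The second breath test is done within 2 weeks of completing therapy, and Visit 2 follows its result, so Visit 2 falls after day 56. Visit 1 is therefore the only scheduled visit inside the course. (Appendix C labels the as-needed digestive enzyme as long term, so that one product may run on past week 8.)

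**2. Does the Visit 0 supply cover the course?** Daily dose × days, against the amount supplied, from the Appendix C product overview:

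- Liver-G.I. Detox: 2 × 30 = 60 of 60 capsules
- L-Glutamine: 2 × 35 = 70 of 73 scoops
- MicroDefense: 1 × 49 = 49 of 90 capsules
- A.C. Formula II: 4 × 49 = 196 of 240 capsules (two bottles of 120)
- Probiotic-5: 1 × 49 = 49 of 60 capsules

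All fixed-dose products are fully covered. Only the as-needed enzyme could run short: 180 / 6 = 30 days at the maximum dose, or 180 / 3 = 60 days at 3 per day.

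**3. How much treatment is still ahead at Visit 1?** Share remaining = dosing days after day 28 / total dosing days, from the Appendix C weekly table:

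| Product | Dosing period | Total days | Days after day 28 | Share |
|---|---|---|---|---|
| A.C. Formula II, MicroDefense, Probiotic-5 | weeks 2–8 | 49 | 28 | 28/49 = 57% |
| L-Glutamine | weeks 2–6 | 35 | 14 | 14/35 = 40% |
| Liver-G.I. Detox | weeks 1–4 plus 2 days | 30 | 2 | 2/30 = 7% |

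For A.C. Formula II this is 4 × 28 = 112 of 196 capsules.

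Visit 1 is only approximately at 4 weeks. Assuming that it may fall one week early or late, the first row becomes (28 + 7)/49 = 35/49 = 71% or (28 − 7)/49 = 21/49 = 43%.

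**The case against.** The strongest reply is that nothing here is wrong or contradictory. Exclusions 3 and 4 are entry criteria, they are applied at entry, and the Risk section says that it relies on enrollment criteria. That is correct. A reader might infer that the Protocol contradicts itself or breaks its own exclusion rule; the text does not support this. The point is only that an existing visit is poorly used.

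A reader might also infer that pregnancy during the study is ignored. It is not. Appendix A's 4-month question outlasts the estimated 12-week study, and the urine test covers status at entry. Other supplements are stopped, continuing drugs must be free of known contraindications, and there is a phone route to the clinic. These narrow the gap to a recognised unplanned pregnancy or a newly started drug that goes unmentioned. The phone route is framed around adverse events, which neither a pregnancy nor a new prescription is in itself.

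The consent form may tell patients to report such changes. The Protocol promises "full and adequate verbal and written information using the IRB approved informed consent documentation", and the form is not among the documents, so it cannot be said that patients receive no such instruction. For that reason no extra patient handout is proposed. What Visit 1 asks is unaffected either way.

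It can fairly be added that the visit list is not declared exhaustive and that a careful clinician may ask anyway. That is true, but nothing requires the question to be asked or the answer recorded.

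Finally, it is tempting to say that any drug on the Appendix A list should halt treatment. The documents do not go that far. Appendix A does not state that a yes excludes, and exclusion 4 reaches only major interactions. The list includes dextromethorphan, sold as a cough remedy, so an automatic hold would be stricter than the entry rule.

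**Conclusion.** The point holds as a minor, optional safety improvement. Pregnancy, breast-feeding and interacting drugs are checked at Visit 0 alone, and the one scheduled visit during the course asks about none of them. At that visit 57% of the dosing days remain for three products (43% to 71% if the visit shifts by a week), 40% for L-Glutamine and 7% for Liver-G.I. Detox.

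These shares show that Visit 1 is early enough for a question to be useful. They are not a risk estimate: the documents give no rate of pregnancy or of new drugs and do not say which product interacts with which drug. The benefit is limited to a change that the patient already knows of by Visit 1 and has not mentioned. A question will not find an unrecognised pregnancy, and later changes still depend on the patient reporting them. Treating the drug list as a guide to exclusion is an inference from exclusion 4. No analysis, endpoint or stated figure is affected.

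**What to change.** Add to Visit 1 in Study Procedures:

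- Repeat the Appendix A questions on pregnancy/breast-feeding and on listed medications, and record the answers.
- If the patient is pregnant or breast-feeding, stop the supplements.
- If a listed drug has been started since Visit 0, the investigator reviews it and records a decision. The affected products are held or stopped only if the interaction is judged major, which is the exclusion 4 standard.

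The cost is two questions at an existing visit and possibly an occasional incomplete course among about 10 patients. Because the second breath test is timed from completion of therapy, the stop date should be noted in such a case. No new visit, procedure or staff is needed.

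### The second breath test is timed from completing the supplements and the final questionnaire from that test's result, so patients who stop early or return no test have no scheduled end-point

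*Protocol*

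**What the plan says.** The study is single-arm, "with an estimated sample size of 10 patients" (Protocol, Study Synopsis). Under Study Procedures, "The supplement protocol is designed to take 8 weeks", and the whole investigation is put at about 12 weeks.

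The end-point measurements are set out under Visits 1 and 2:

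- "Visit 1 will occur approximately 4 weeks after the patient begins the supplement protocol". At that visit "Patients will be provided with the second lactulose breath test kit", and they are "instructed to perform the test within 2 weeks of completing the supplement therapy". A questionnaire is also completed there, while treatment is still running.
- "Visit 2 will occur after the results of the post-treatment breath test are available". The questionnaire at Visit 2 is the only one after treatment ends; the other two are at baseline and at Visit 1.

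Under Data Management, breath test scores and questionnaires "will be compared pre- and post-treatment to determine the efficacy of the supplement therapy". Significance is to be tested only if the final sample size allows it.

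Study Oversight foresees withdrawals: "This study will be terminated if one-half or more of enrolled patients withdraw due to adverse events". The protocol describes no early-termination visit, no test or questionnaire for a patient who stops the supplements early, and no calendar window for Visit 2.

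**The concern.** Each end-of-study measurement waits on an earlier step. The test waits on finishing the supplements, and the final questionnaire waits on the test. A patient who misses one step has no scheduled place in what follows, and a missed breath test can take the symptom outcome with it, although the questionnaire does not depend on a breath result.

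Patients who stop because of side effects or lack of benefit are less likely to be improved. Several of the side effects listed under Monitoring/Reporting, such as diarrhea, constipation and bloating, are also items of the questionnaire and symptoms of the condition. Losing these patients from an uncontrolled pre/post comparison would tend to flatter the result, and there is no control arm in which the same loss would show. The Background hopes to improve on earlier treatments with response rates below one half, and the results, if favourable, are intended for advertising.

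This is a rule about what is collected. A statistical analysis plan, which is not at hand, could decide how to count patients without an end-point, but it could not recover a measurement that was never taken.

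**Working it through.** **Step 1. Follow each kind of patient through the schedule as written.**

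| Patient | Second breath test | Final questionnaire |
|---|---|---|
| Finishes the supplements and returns the test | Scheduled | Scheduled, once the result is in |
| Leaves before Visit 1 (about week 4) | No kit | None scheduled |
| Stops the supplements after Visit 1 | Kit in hand, but its timing counts from completion, so none scheduled | None scheduled; a week-4 score exists but is on-treatment |
| Finishes but returns no test | Missing | None scheduled, because Visit 2 waits on the result |

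Only the first row has both post-treatment values that the comparison in Data Management needs.

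**Step 2. Is there a figure of the plan to reproduce?** No. The sample size of 10 is an estimate. No drop-out rate, expected response or responder definition is given, so the size of any bias cannot be derived from the protocol.

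**Step 3. How the bias would arise.** Let N = 10 be enrolled, m have no end-point, and p_t and p_m be the response proportions in the tested and the missing. The rate in all enrolled is [(N − m)p_t + m·p_m]/N. The tested rate differs from it by

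bias = (m/N)(p_t − p_m).

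It is upward when the missing respond less often than the tested, and zero when they respond equally.

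**Step 4. Illustration.** Assumed, not from the protocol: m = 2, with 4 responders among those tested.

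- Among those tested: 4/8 = 50% (exact 95% interval 16% to 84%).
- Among all enrolled, if neither missing patient responded: 4/10 = 40% (12% to 74%). Bias = (2/10)(0.50 − 0) = 10 percentage points.
- If both missing patients responded: 6/10 = 60%. Bias = (2/10)(0.50 − 1) = −10 points.

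**Step 5. Range over the assumed number missing, with 4 responders among those tested.**

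| Missing | Rate in tested | All enrolled, missing as non-responders | All enrolled, missing as responders |
|---|---|---|---|
| 0 | 4/10 = 40% | 40% | 40% |
| 1 | 4/9 = 44% | 40% | 50% |
| 2 | 4/8 = 50% | 40% | 60% |
| 3 | 4/7 = 57% | 40% | 70% |
| 4 | 4/6 = 67% | 40% | 80% |

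If every missing patient is a non-responder, the tested rate exceeds the enrolled rate by the factor 10/(10 − m), from 1.11 with one missing to 1.67 with four.

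**The case against.** The visit wording can be read as timing instructions and not as exclusions. Nothing forbids a patient who stops after Visit 1, kit in hand, from testing, and nothing says that Visit 2 is cancelled if no test is returned. The Synopsis offers the post-treatment test free to enrolled patients without limiting it to completers. Everyone who reaches week 4 has a questionnaire, and adverse events can be reported by phone, so such patients are not without data. This stands as far as it goes: the defect is that nothing is scheduled for them, not that they are barred. Only a patient who leaves before Visit 1 clearly gets no kit.

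Two stronger readings are tempting, and the document supports neither.

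- **That efficacy will be judged on completers only.** No analysis population is named. A tendency towards completers follows from the schedule but is not a stated rule, and the choice of population belongs to the analysis plan. A poorly compliant patient who finishes and returns a test is still included.
- **That the flaw is worth 67% against 40%.** The termination rule is met at 5 of 10, so 4 adverse-event withdrawals leave the study running, and 4 responders among the other 6 would give 67%. But the responder count is assumed, the maximum number of withdrawals is chosen, and every withdrawal is counted as a failure. The protocol also does not separate stopping the supplements from leaving the study. Patients who have left would not be recovered by re-timing a visit, so much of that gap would reflect withdrawal and the choice of denominator. The response rate below one half in the Background is motivation, not a success criterion.

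The upward direction is likely but not certain. A patient who finishes and returns no test may feel well. Visit 2 is not among the items provided free, so cost may also keep people away whatever their outcome.

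**Conclusion.** The point holds as a gap in data collection. As written, the schedule gives no breath test to patients who stop the supplements early and no final questionnaire to those who return no test. The pre/post comparison will therefore tend to rest on patients who finish and return a test, and is probably biased upward.

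The protocol's figures do not determine the amount. The 50% of 8 tested against 40% of 10 enrolled is an illustration that assumes two missing patients, four responders and no response among the missing. With the same counts, the rate in all enrolled could lie anywhere from 40% to 60%, and the exact intervals for 4/8 and 4/10 overlap almost wholly. In a pilot of this size the gap does not invalidate the study, but it is worth closing because the measurements cannot be recovered afterwards.

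**What to change.** Amend Visits 1 and 2 under Study Procedures, and the matching sentence of the Synopsis:

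- Schedule the second breath test and the final questionnaire in a fixed window counted from the start of the protocol, for every enrolled patient still willing, whether or not the supplements were completed. For a patient who finishes on time, the present wording already amounts to weeks 8 to 10 (8 + 2 = 10), inside the stated 12 weeks.
- Give or send the kit to anyone who stops before Visit 1.
- Collect the final questionnaire in that window even if no breath result arrives. Appendix B already has it administered online.
- Report the number enrolled alongside the number with each end-point.

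These changes concern measurement only and leave treatment untouched. The cost is a small amendment to the visit wording, submitted to the IRB as the protocol requires. The test is already offered free to enrolled patients. The result may turn out less favourable, and patients who have left the study altogether will still be missing.

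### The only post-course symptom questionnaire is at Visit 2, after the second breath-test result is back, and nothing requires it to be completed before the patient hears that result

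*Protocol*

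**What the plan says.** Under Study Procedures the MSQ is completed at Visit 0 (baseline), Visit 1 (about week 4) and Visit 2. The last visit is timed only by this rule: "Visit 2 will occur after the results of the post-treatment breath test are available". There the investigator "will interpret the results of the second breath test, and patients will be asked to complete the Medical Symptom Questionnaire". No latest day is given. The second test kit is handed out at Visit 1, for use within the 2 weeks that follow the course.

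The same section gives two durations: "The supplement protocol is designed to take 8 weeks" and "Due to the delay in receiving and interpreting test results, the investigation, in its entirety, is estimated to take 12 weeks".

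Data Management makes the form an efficacy measure: "Lactulose breath test scores and completed Medical Symptom Questionnaire will be compared pre- and post-treatment to determine the efficacy of the supplement therapy". The Study Synopsis describes an open-label study "with an estimated sample size of 10 patients" and adds: "No control group will be assigned".

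At baseline, Visit 0 opens with the investigator's assessment of the first breath test and the discussion of treatment options. Consent and the baseline MSQ come later in that visit. The inclusion criterion requires symptoms and "positive results of a lactulose breath test". Appendix B has the MSQ administered online, and its printed copy shows no recall period.

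**The concern.** The MSQ is a self-rating. With no blinding and no control group, nothing separates a treatment effect from expectation, so the rating is already exposed. The Visit 2 schedule allows a second, avoidable influence. A patient told that the breath test has turned negative may rate symptoms lower, and one told that it is still positive may rate them higher. The two efficacy measures would then be linked by disclosure, and a reader who takes symptom improvement as independent support for the breath-test change would be misled. No later analysis can recover a rating made before disclosure if none was collected.

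Timing is a lesser point. The rating date follows the sample date by an interval that the protocol neither fixes nor records, so it can differ between patients.

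**Working it through.** **1. Which questionnaire is post-course?** Visit 0 precedes the course, Visit 1 falls at about week 4 of 8, and Visit 2 follows the second result. So 1 of 3 scheduled forms per patient is post-course.

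Visit 1 cannot stand in for it. In Appendix C, three products (MicroDefense, A.C. Formula II, Probiotic-5) are listed for 49 days and run from week 2 to week 8 (7 × 7 = 49). By the end of week 4 they have been taken for 3 × 7 = 21 days, and 21/49 = 43%.

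**2. When does Visit 2 fall?** The 12-week estimate cannot be rebuilt, because neither its starting point nor the laboratory delay is given. The available inputs are:
- course end: week 8;
- second breath test, reading its window as running after completion: week 8 to 8 + 2 = week 10;
- Visit 2: some time after the result is back.

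If the 12 weeks run from first intake and Visit 2 falls at week 12, the gap from sample to rating is 12 − 10 = 2 to 12 − 8 = 4 weeks. Any time before first intake that the estimate includes shortens this gap. If the estimate is overrun, the text sets no upper limit.

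**3. Baseline and follow-up side by side.**

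| | Baseline (Visit 0) | Follow-up (Visit 2) |
|---|---|---|
| Breath result in hand before the visit's MSQ | yes | yes |
| Patient told before rating | implied: diagnosis and treatment options come before consent and MSQ | not fixed |
| Result | positive in every enrolled patient | can differ between patients |
| Limit on sample-to-rating gap | none stated | none stated |

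**4. Does the matching order cancel the effect?** Higher MSQ item scores are worse. Suppose that knowing a positive result adds *b* to the score and knowing a negative one subtracts *c* (both zero or more, sizes unknown), and that a proportion *p* of patients turn negative. The shift in post-minus-pre change is:
- told before rating, second test positive: *b* − *b* = 0;
- told before rating, second test negative: −*c* − *b* = −(*b* + *c*);
- rated before disclosure, any result: 0 − *b* = −*b*.

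So the order cancels only for patients who stay positive. If all are told first, the shift depends on the second result and averages −*p*(*b* + *c*). If all rate before disclosure, it is −*b* whatever the result. The latter is smaller in size only when (1 − *p*)*b* < *pc*. If *b* = 0, rating first removes the shift entirely; if *c* = 0, it does not reduce it. The protocol gives no value for *b*, *c* or *p*.

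**5. Cost of a lost form.** With 10 planned patients there are 10 × 3 = 30 scheduled forms, of which 10 are post-course. One missed post-course form is 1/10 = 10% of the post-course forms and 1/30 = 3.3% of all forms.

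**The case against.** The best reply is that nothing here is shown to go wrong. The Visit 2 sentence joins interpretation and questionnaire without ordering them, and an online form can be completed before any discussion. That stands: a reader might infer that patients are told first, and the protocol does not say so. Awareness is possible, not established.

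Second, the follow-up repeats the baseline order of test, result, visit and form. This also stands, and a reader should not infer that the follow-up is handled less carefully than baseline. It does not dispose of the point, because the first result was the same for everyone and the second need not be. It does mean that a change at follow-up breaks the symmetry, and the working shows that a smaller bias in the mean change cannot be promised.

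Third, a reader might infer that the gap between sample and rating is open-ended and damages the analysis. The 12-week figure gives an expected time, though not a visit window, and the protocol states no paired or correlation analysis of the two measures. Without a printed recall period, equal dates would not guarantee that the same symptom period is rated. The gap is therefore a reason to record dates, not a demonstrated harm.

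Finally, this is a pilot of about 10 patients that is already open to expectation. That limits the weight of the point, but the order of assessments is set in Study Procedures and cannot be repaired by an analysis plan.

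**Conclusion.** The point holds as a gap in the visit schedule. The sole post-course self-rating is collected when a patient-specific result already exists, with no safeguard on disclosure and no latest day. It concerns one of the two efficacy measures in an open-label, uncontrolled study.

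The size of any bias cannot be derived from the protocol. The 2-to-4-week gap between sample and rating holds only if the 12 weeks start at first intake and Visit 2 is at week 12.

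Rating before disclosure makes the follow-up score independent of knowledge of the second result. It protects only that half of the comparison: a baseline rated after a positive result would be set against a follow-up rated before any second result. This has to be stated when reporting. The change should be made because it costs little and what it prevents cannot be undone later. Confidence is medium, since disclosure before rating is permitted rather than prescribed.

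**What to change.** Amend Visits 1 and 2 as follows:
- Require the post-treatment MSQ to be completed online before the second breath-test result is disclosed, preferably on the day of that test and before the lactulose is taken.
- If it is missed, have it completed at the start of Visit 2, before any result is disclosed.
- Leave compliance and adverse-event reporting at Visit 2.
- Record the dates of course completion, breath test and MSQ, and report how many forms came by each route.
- When reporting, state that the baseline MSQ followed the first breath result and the follow-up MSQ preceded disclosure of the second.

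No extra visit or procedure is needed, since the form is already online. The costs are a patient reminder for the test day and IRB approval of the wording before use. There may also be two rating times among about 10 patients, and a back-up form keeps the present time gap. For forms completed on the test day the follow-up gap is 0 days; the baseline gap is unchanged, and the test day can still vary within its 2-week window.
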